5.1.1 Intention-to-Treat (ITT) Population

All randomized subjects who receive at least one dose of study drug in the DB Treatment Period will be included in the ITT population. The data from the ITT population will be presented by the treatment arm assigned at the time of randomization (Arm A or Arm B).

Efficacy analyses and analyses of compliance data will be performed on the ITT population, unless otherwise specified. If the ITT population differs from the safety population (as described in Section 5.1.3), analyses of demographics and baseline characteristics will also be performed on the ITT population by treatment arm.

5.1.2 Modified Intention-to-Treat (mITT) Populations

Sensitivity analyses of SVR₁₂ as described in Section 10.5, when applicable, will be performed on the ITT population modified to exclude subjects who have multiple GTs according to the central laboratory or phylogenetic analyses of the baseline sample or subjects who received an incorrect duration of treatment due to incorrect classification of

GT or treatment experience at randomization (mITT-GT), and on the mITT-GT population modified to exclude subjects who did not achieve SVR₁₂ for reasons other than virologic failure (i.e., subjects with reasons other than on-treatment HCV virologic failure and relapse) (mITT-GT-VF).

5.1.3 Safety Population

All subjects who receive at least one dose of study drug in the DB Treatment Period will be included in the safety population. Analyses of safety; demographics; baseline characteristics; medical history; prior, concomitant, and post-treatment medications; and study drug exposure will be performed on the safety population according to actual treatment received during the DB Treatment Period even if this differs from the randomized treatment assignment; i.e., subject grouping will be based on the actual treatment received, not the arm to which the subject was randomized. If all subjects take the treatment to which they were randomly assigned, the safety population will be presented in the same way as the ITT population.

5.1.4 Open-Label (OL) Population

All subjects randomized to Arm B who receive at least one dose of active, OL study drug during the OL Treatment Period will be included in the OL population. All analyses of data collected for subjects in Arm B during and after the OL Treatment Period will be performed on the OL population.

5.2 Variables Used for Stratification of Randomization

Randomization of subjects will be stratified by geographic region (China, Singapore and South Korea), genotype (GT1, GT2, combined GT3 – 6), and HCV/HIV co-infection status (yes, no).

If a subject was randomized based on incorrect stratification information, the correct stratification information (if known at the time of the primary SVR₁₂ analysis) will be used to define subpopulations for analyses.

6.0 Analysis Conventions

6.1 Definition of Baseline, Final Treatment, and Final Post-Treatment Assessments

6.1.1 Baseline

The baseline value refers to the last non-missing measurement collected before the first dose of study drug is received. The protocol specifies that all Day 1 assessments (other than intensive PK samples) are to be performed prior to administering the first dose of study drug. Therefore, all Day 1 assessments for which time is not collected will be assumed to be pre-dose and the baseline value will be the last non-missing measurement collected on or before the first day of study drug administration.

All Day 1 assessments with time available must be before the time of first dose to be considered baseline, and the last non-missing measurement collected before the date and time of the first dose of study drug will be considered the baseline value. Only for resistance analyses, the last sample collected before OL Day 1 will be considered the baseline value for Arm B subjects. If multiple measurements that are prior to dosing are recorded on the same date and with the same time or if time is not available, then the average of these measurements will be considered the baseline value. The same baseline value will be used for analyses of the Treatment and PT Periods.

Safety assessments that are related to a serious adverse event that occurred on the first dose day are excluded when applying this algorithm.

6.1.2 Study Days

DB Study Days (Days Relative to the First Dose of DB Study Drug)

DB study days are calculated for each time point in the DB Treatment Period relative to the first dose of DB (active or placebo) study drug. Study days are negative values when the time point of interest is prior to the first DB study drug dose day. Study days are positive values when the time point of interest is after the first DB study drug dose day.

There is no DB Study Day 0. DB Study Day 1 is the day of the first dose of DB study drug in the DB Treatment Period.

DB Study Drug End Days (Days Relative to the Last Dose of DB Study Drug)

Study drug end days are calculated for each time point relative to the last dose of DB study drug. The last day of DB study drug dosing is defined as DB Study Drug End Day 0. Days before it have negative study drug end days and days after it have positive study drug end days.

Active Study Days (Days Relative to the First Dose of Active Study Drug)

Active Study Days will be defined for all subjects who receive at least one dose of ABT-493/ABT-530 (DB or OL) study drug.

Active Study Day 1 is the day of the first dose of active study drug. For subjects randomized to Arm A, DB Study Days and Active Study Days are equivalent. For subjects randomized to placebo (Arm B) and in the OL population, Active Study Days are based on the first dose of OL active study drug.

Active Study Drug End Days (Days Relative to the Last Dose of Active Study Drug)

Active study drug end days are calculated for each time point relative to the last dose of ABT-493/ABT-530 (DB or OL) study drug. The last day of active study drug dosing is defined as Active Study Drug End Day 0. Days before it have negative study drug end days and days after it have positive study drug end days.

For subjects randomized to Arm A, DB Study Drug End Days and Active Study Drug End Days are equivalent. For subjects randomized to placebo (Arm B) and in the OL population, Active Study Drug End Days are based on the last dose of OL active study drug.

Final Treatment Value

The final treatment value is defined as the last non-missing measurement collected after Study Day 1 dosing time within a treatment period as defined below.

During the DB Treatment Period, the Final DB Treatment Value is defined separately for placebo and active subjects. Subjects randomized to placebo (Arm B) should take the first dose of OL study drugs the day immediately after the last day of the DB Treatment Period. Therefore, for Arm B subjects, the Final DB Treatment Value is defined as the last non-missing measurement collected after DB Study Day 1 and no more than 2 days after the last dose of placebo and before OL Day 1 (if applicable). For subjects randomized to active study drug (Arm A), the Final DB Treatment Value is defined as the last non-missing measurement collected after DB Study Day 1 and within 2 days of the last dose of active study drug (i.e., on or before Active Study Drug End Day 2).

During the OL Treatment Period, for subjects randomized to placebo who receive OL study drug, the Final OL Treatment Value is defined as the last non-missing measurement collected after OL Day 1 and on or before Active Study Drug End Day 2.

Final Post-Treatment Value

The final PT value for each subject is the last non-missing measurement collected after Active Study Drug End Day 2 and on or before Active Study Drug End Day 999.

6.2 Definition of Analysis Windows

For efficacy analyses of HCV RNA and resistance, the time windows specified in [Table 4](#), [Table 5](#) and [Table 6](#) describe how efficacy data are assigned to protocol-specified time points during the DB Treatment, OL Treatment, and PT Periods, respectively. All time points and corresponding time windows are defined based on the date/time of blood sample collection.

For safety laboratory data, vital signs, and PRO instruments, the time windows specified in [Table 4](#), [Table 5](#) and [Table 7](#) describe how data are assigned to protocol-specified time points.

For samples of plasma HIV-1 RNA and flow cytometry (including but not limited to CD4+ T-cell and CD8+ T-cell counts [absolute and percent]), the time windows specified in [Table 8](#), [Table 9](#), and [Table 10](#) describe how data are assigned to protocol-specified time points.

If more than one assessment is included in a time window, the assessment closest (except in analyses of SVR) to the nominal time will be used. If there are two observations equally distant to the nominal time, the latest one will be used in analyses. For analyses of SVR (e.g., SVR₁₂), the last value in the window will be used.

If multiple measurements are made on the same day for a safety laboratory parameter, a vital sign parameter, or a flow cytometry parameter, the average of the values will be used to calculate descriptive statistics and in analyses of the mean change from baseline. For summaries of shifts from baseline, graded laboratory values and potentially clinically significant values, multiple values on the same day will not be averaged; all values will be considered for these analyses.

Table 4. Analysis Time Windows for HCV RNA and Resistance Endpoints, Safety Laboratory and Vital Sign Measurements, and PRO Instruments (DB Treatment Period)

Scheduled Visit	Nominal Day (DB Study Day)	Time Window (DB Study Day Range)
DB Day 1/Baseline ^a	1 ^a	≤ 1 ^a
DB Week 1	7	2 to 10
DB Week 2	14	11 to 21
DB Week 4	28	22 to 42
DB Week 8	56	43 to 70
DB Week 12 ^b	84	71 to 98
DB Week 16 ^b	112	99 to 126
Final DB Treatment Visit ^c	2 to ≤ 2 days after last dose of DB study drug	

a. Day of first dose of DB study drug.

b. For 16-week treatment only.

c. The last value within the window will be used to define the Final DB Treatment Visit value. For Arm A subjects, the upper bound of this Final window is DB Study Drug End Day 2. For Arm B subjects, it is the earlier of DB Study Drug End Day 2 and the day of first dose of OL active study drug. DB Study Drug End Day 0 is defined as the day of the last dose of DB study drug.

Note: For all windows, data must be on or before DB Study Drug End Day 2, and for Arm B subjects data must also be on or before the day of first dose of OL active study drug. The result closest to the scheduled time point will be used. PRO instruments are collected at DB Day 1, DB Week 4, DB Week 12 (if 16-week treatment), and DB End of Treatment Visit.

Table 5. Analysis Time Windows for HCV RNA and Resistance Endpoints and Safety Laboratory and Vital Sign Measurements (OL Treatment Period)

Scheduled Visit ^a	Nominal Day (Active Study Day)	Time Window (Active Study Day Range)
OL Day 1 ^b	1	
OL Week 1	7	2 to 10
OL Week 2	14	11 to 21
OL Week 4	28	22 to 42
OL Week 8	56	43 to 70
OL Week 12 ^c	84	71 to 98
OL Week 16 ^c	112	99 to 126
Final OL Treatment Visit ^d	2 to ≤ 2 days after last dose of OL study drug	

- a. OL visits are applicable for subjects randomized to Arm B (placebo) who received at least one dose of OL active study drug.
- b. Day of first dose of OL active study drug. For resistance analyses only, baseline value for Arm B subjects will use the last sample collected before OL Day 1.
- c. For 16-week treatment only.
- d. The last value within the window will be used to define the Final OL Treatment Visit value. The upper bound of this Final window is Active Study Drug End Day 2. Active Study Drug End Day 0 is defined as the day of the last dose of active study drug.

Note: For all windows, data must be on or before Active Study Drug End Day 2. The result closest to the scheduled time point will be used. PRO instruments are not collected for Arm B subjects during the OL Treatment Period.

Analyses of these data will not be included in the primary CSR.

Table 6. Analysis Time Windows for HCV RNA and Resistance Endpoints (Post-Treatment Period)

Scheduled Visit^a	Nominal Day (Active Study Drug End Day)	Time Window (Active Study Drug End Day Range)
Post-Treatment Week 4	28	3 to 56
Post-Treatment Week 12	84	57 to 126
Post-Treatment Week 24 ^b	168	127 to 999
SVR ₄ ^c	28	3 to 56
SVR ₁₂ ^c	84	57 to 126
SVR ₂₄ ^{b,c}	168	127 to 210

a. PT Visits are applicable for subjects who received at least one dose of active (DB or OL) study drug.

b. Not included in primary CSR; for Arm B, included only in final CSR.

c. For SVR windows, the last value in the window will be used.

Note: The result closest to the scheduled time point will be used, except for SVR₄, SVR₁₂, and SVR₂₄. For all windows, data must occur after Active Study Drug End Day 2. Active Study Drug End Day 0 is defined as the day of the last dose of active study drug.

Analyses of these data for Arm B will not be included in the primary CSR.

Table 7. Analysis Time Windows for Safety Laboratory and Vital Sign Measurements and PRO Instruments (Post-Treatment Period)

Scheduled Visit^a	Nominal Day (Active Study Drug End Day)	Time Window (Active Study Drug End Day Range)
Post-Treatment Week 4	28	3 to 56
Post-Treatment Week 12	84	57 to 126
Post-Treatment Week 24 ^b	168	127 to 999
Final Post-Treatment Visit ^c	> 2 days after last dose of active study drug	

a. PT Visits are applicable for subjects who received at least one dose of active (DB or OL) study drug.

b. Not included in primary CSR; for Arm B, included only in final CSR.

c. The last value within the PT Period window will be used to define the Final PT Visit value. The lower bound of this Final window is Active Study Drug End Day 3. Active Study Drug End Day 0 is defined as the day of the last dose of active study drug.

Note: The result closest to the scheduled time point will be used. For all windows, data must occur after Active Study Drug End Day 2. Vital signs are collected at every PT visit; hematology, chemistry, urinalysis, and coagulation panels are collected at PT Week 4 or PT D/C (if subject discontinued prior to PT Week 4); PRO instruments are collected for Arm A subjects only and only at PT Week 12 and PT Week 24 (or PT D/C).

Analyses of these data for Arm B will not be included in the primary CSR.

Table 8. Analysis Time Windows for HIV-1 RNA and Flow Cytometry Measurements (DB Treatment Period)

Scheduled Visit	Nominal Day (DB Study Day)	Time Window (DB Study Day Range)
DB Day 1/Baseline ^a	1 ^a	≤ 1 ^a
DB Week 2	14	2 to 21
DB Week 4	28	22 to 42
DB Week 8	56	43 to 70
DB Week 12 ^b	84	71 to 98
DB Week 16 ^b	112	99 to 126
Final DB Treatment Visit ^c	2 to ≤ 2 days after last dose of DB study drug	

- a. Day of first dose of DB study drug.
b. For 16-week treatment only.
c. The last value within the window will be used to define the Final DB Treatment Visit value. For Arm A subjects, the upper bound of this Final window is DB Study Drug End Day 2. For Arm B subjects, it is the earlier of DB Study Drug End Day 2 and the day of first dose of OL active study drug. DB Study Drug End Day 0 is defined as the day of the last dose of DB study drug.

Note: Time windows specified in this table are for HCV/HIV co-infected subjects only. For all windows, data must be on or before DB Study Drug End Day 2, and for Arm B subjects, data must also be on or before the day of first dose of OL active study drug. The result closest to the scheduled time point will be used. Flow cytometry samples are collected at DB Day 1, DB Week 4, DB Week 12 (if 16-week treatment), and DB End of Treatment Visit.

Table 9. Analysis Time Windows for HIV-1 RNA and Flow Cytometry Measurements (OL Treatment Period)

Scheduled Visit ^a	Nominal Day (Active Study Day)	Time Window (Active Study Day Range)
OL Week 1	7	2 to 10
OL Week 2	14	11 to 21
OL Week 4	28	22 to 42
OL Week 8	56	43 to 70
OL Week 12 ^b	84	71 to 98
OL Week 16 ^b	112	99 to 126
Final OL Treatment Visit ^c	2 to ≤ 2 days after last dose of OL study drug	

- a. OL visits are applicable for subjects randomized to Arm B (placebo) who received at least one dose of OL active study drug.
b. For 16-week treatment only.

Table 9. Analysis Time Windows for HIV-1 RNA and Flow Cytometry Measurements (OL Treatment Period) (Continued)

c. The last value within the window will be used to define the Final OL Treatment Visit value. The upper bound of this Final window is Active Study Drug End Day 2. Active Study Drug End Day 0 is defined as the day of the last dose of active study drug.

Note: Time windows specified in this table are for HCV/HIV co-infected subjects only. For all windows, data must be on or before Active Study Drug End Day 2. The result closest to the scheduled time point will be used. Flow cytometry samples are collected at OL Week 4, OL Week 12 (if 16-week treatment), and OL End of Treatment Visit.

Analyses of these data will not be included in the primary CSR.

Table 10. Analysis Time Windows for HIV-1 RNA and Flow Cytometry Measurements (Post-Treatment Period)

Scheduled Visit ^a	Nominal Day (Active Study Drug End Day)	Time Window (Active Study Drug End Days Range)
Post-Treatment Week 4	28	3 to 56
Post-Treatment Week 12	84	57 to 126
Post-Treatment Week 24 ^b	168	127 to 999
Final Post-Treatment Visit ^c	> 2 days after last dose of active study drug	

a. PT Visits are applicable for subjects who received at least one dose of active (DB or OL) study drug.

b. Not included in primary CSR; for Arm B, included only in final CSR.

c. The last value within the PT Period window will be used to define the Final PT Visit value. The lower bound of this Final window is Active Study Drug End Day 3. Active Study Drug End Day 0 is defined as the day of the last dose of active study drug.

Note: Time windows specified in this table are for HCV/HIV co-infected subjects only. The result closest to the scheduled time point will be used. For all windows, data must occur after Active Study Drug End Day 2.

Analyses of these data for Arm B will not be included in the primary CSR.

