**Methodology (Continued):**

In the OL Treatment Period, visits will occur at Weeks 1, 2, 4, 8, 12, and 16 for subjects assigned to receive 16 weeks of treatment; for subjects assigned to receive 8 weeks of treatment, scheduled visits will occur at Weeks 1, 2, 4 and 8. OL Day 1 will be the day after the final scheduled DB visit (Week 8 or Week 16) and subjects will not return for a visit; rather, the subjects will be instructed to take their first dose of ABT-493/ABT-530 at home. Study procedures, including assessment of adverse events, vital signs, adherence, concomitant medications, HCV RNA, HCV resistance, HIV-1 RNA and HIV resistance (as applicable), pharmacokinetic assays, and clinical laboratory tests will be conducted at each visit.

Post-Treatment (PT) Period: Subjects randomized to active drug (Arm A) who complete or prematurely discontinue study drug during the DB Treatment Period and subjects randomized to placebo (Arm B) who complete the OL Treatment Period or prematurely discontinue study drug during the OL Treatment Period, will be followed for 24 weeks to monitor safety and to evaluate efficacy and the emergence and/or persistence of HCV resistance-associated substitutions (RASs).

Baseline HCV resistance samples will be collected for all subjects, but HCV resistance analysis of baseline and post-baseline samples will be performed only for subjects who experience virologic failure. During the PT Period, all subjects will have visits at Weeks 4, 12, and 24 following completion of either the DB Treatment Period (for subjects randomized to ABT-493/ABT-530 in the DB Treatment Period) or the OL Treatment Period (for subjects randomized to placebo in the DB Treatment Period). Study procedures to monitor safety, HCV RNA, HIV-1 RNA and HIV resistance (as applicable), and the emergence and/or persistence of HCV resistance-associated substitutions will be conducted during these visits.

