### **5.1.3 Open-Label Treatment Period**

After completing the DB Treatment Period, subjects initially randomized to placebo (Arm B) at the beginning of the DB Treatment Period will receive 8 or 16 weeks of open-label ABT-493/ABT-530. Subjects will be provided dosing instructions and will be dispensed study drug at the final scheduled DB Treatment Period visit (Week 8 or Week 16). Administration of ABT-493/ABT-530 will start the next day (OL Day 1). The same type of bottles as used for placebo will be used for active study drug ABT-493/ABT-530.

Sites must call subjects within 4 days after the final scheduled DB Treatment Period visit (Week 8 or Week 16) to verify the first day of open-label, study drug administration and record this date on the eCRF and in the source documents. Study drugs, virologic results and safety laboratory results will not be blinded during the OL Treatment Period. Virologic failure criteria and toxicity management will be evaluated and applied by the investigator (Section 5.4.1.1 and Section 6.1.7).

Subjects who prematurely discontinue from the OL Treatment Period should return for a Treatment D/C Visit and undergo the study procedures as defined in Appendix C and as described in Section 5.4.1. Ideally, this should occur on the day of study drug discontinuation, but is recommended to be no later than 2 days after their final dose of study drugs and prior to the initiation of any other anti-HCV therapy. Subjects who complete or discontinue the OL Treatment Period will be monitored for safety, HCV RNA, the emergence and persistence of resistant viral variants, plasma HIV-1 RNA and HIV resistance (as applicable) in the 24-week Post-Treatment Period as detailed in Section 5.1.4.

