## **5.3.2 Drug Concentration Measurements**

### **5.3.2.1 Collection of Samples for Analysis**

Blood samples for pharmacokinetic assay of ABT-493, possible ABT-493 metabolites, ABT-530, possible ABT-530 metabolites and HIV-1 ART regimens will be collected by venipuncture at each study visit during the DB or OL Treatment Periods as indicated in [Appendix C](#).

Subjects who do not participate in Optional Intensive PK sampling:

- At all DB and OL Treatment Period visits, except for Day 1, a single blood sample (3 mL) will be collected for ABT-493/ABT-530 without regard to the time of dosing. For co-infected subjects only, an additional blood sample (4 mL) will be collected for possible HIV-1 ART assays.
- The date and time of blood sample collection and the two previous doses of the study drug will be recorded to the nearest minute in the source documents. Additionally, the date and time of the two previous doses of the study drug will be recorded to the nearest minute on the eCRF.

Subjects who consent to participate in Optional Intensive PK sampling:

- On DB Day 1 and the DB and OL Week 4 visits, subjects will have their dose administered by study site personnel after food. Blood samples (3 mL each) will be collected on DB Day 1 at 2, 4 and 6 hours post-dose and at the DB and OL Week 4 Visits immediately prior to dose (0 hour) and 2 and 4 hours post-dose. For co-infected subjects only, an additional blood sample (4 mL) will be collected at each timepoint for possible HIV-1 ART assays.
  - The date and time of site-administered dose, blood sample collection and the two previous doses of study drug (for Week 4 Visit only) will be recorded to the nearest minute in the source documents. Additionally, the date and time of the site-administered dose and two previous doses (for Week 4 Visit only) will be recorded in the eCRF.
- At all other DB and OL Treatment Period visits, a single blood sample (3 mL) will be collected for ABT-493/ABT-530 without regard to the time of dosing. For co-infected subjects only, an additional blood sample (4 mL) will be collected for possible HIV-1 ART assays.
  - The date and time of blood sample collection and the two previous doses of the study drug will be recorded to the nearest minute in the source documents. Additionally, the date and time of the two previous doses of the study drug will be recorded to the nearest minute on the eCRF.

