**Open-Label Treatment Period**

Activity	Day 1	Week 1	Week 2	Week 4	Week 8*	Week 12 #	Week 8 EOT/Week 16 EOT or Premature D/C from Treatment a
First Dose of Active Drug	X b						
Physical Examination							X
Vital Signs, Weight	X	X	X	X	X	X	X
12-lead ECG							X
Hematology/Chemistry/Urinalysis/Coagulation Panel	X	X	X	X	X	X	X
Pregnancy Test (urine [u]) c		X (u)	X (u)	X (u)	X (u)	X (u)	X (u)
Concomitant Medication Assessment	X	X	X	X	X	X	X
Adverse Event Assessment d	X	X	X	X	X	X	X
Dispense Study Drug				X	X e	X	
Study Drug Accountability f and Review of Study Drug Adherence	X	X	X	X f	X f	X f	X f
HCV RNA Sample	X	X	X	X	X	X	X
HIV-1 RNA g,h	X	X	X	X	X	X	X
HCV Resistance Sample	X	X	X	X	X	X	X
Archive Plasma Sample	X	X	X	X	X	X	X
Flow Cytometry Sample g				X		X	X
Pharmacokinetic Samples for subjects who do not participate in the Optional Intensive PK sampling i	X	X	X	X	X	X	X
Pharmacokinetic Samples for subjects who do participate in the Optional Intensive PK sampling i	X	X	X	X j	X	X	X

EOT = End of treatment; D/C = Discontinuation

\* The EOT visit can be at Week 8 or Week 16 depending on treatment assigned.

- # Applicable only to those subjects enrolled into a 16-week treatment.
- a. Subjects who prematurely discontinue the OL Treatment Period should return to the site to complete the Premature D/C Visit Procedures (preferably prior to the initiation of any other anti-HCV therapy).
- b. Subjects will take the first dose of Open-Label study drugs the day after the last day of the DB Treatment Period. The site will call the subject and record the study drug start date in the EDC system and source documents. The study drug end date of drug will be recorded in EDC and the source at OL Week 8 EOT/Week 16 EOT or Premature D/C from treatment.
- c. Pregnancy testing is not required for females of non-childbearing potential as defined in Inclusion Criterion 3.
- d. See specific information regarding adverse event collection in Section 6.1.4.
- e. Applicable only to those subjects enrolled into a 16-week treatment.
- f. Subjects should bring all the study drug to the study drug accountability visits at Weeks 4, 8, 12, EOT or Premature D/C. The site will record the number of tablets returned at these visits.
- g. HCV/HIV co-infected subjects only.

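### The SAP gives two different cut-offs for Arm B double-blind data: section 6.1.2 excludes OL Day 1, Tables 4 and 8 admit it with no pre-dose condition, and the protocol contradicts itself on whether samples are taken that day.

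*SAP*

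**What the plan says.** **SAP.** Section 6.1.2 (Final Treatment Value) limits the Arm B Final DB Treatment Value to measurements "no more than 2 days after the last dose of placebo and before OL Day 1 (if applicable"). Section 6.2 sets the bound for the same value differently. Footnote c of Tables 4 and 8 puts the Arm B upper limit at DB Study Drug End Day 2 or the day of the first open-label active dose, whichever is earlier, and takes the last value in the window. The Table 4 Note extends the inclusive bound to every double-blind window: "for Arm B subjects data must also be on or before the day of first dose of OL active study drug". The Table 8 Note does the same for HIV-1 RNA and flow cytometry: "for Arm B subjects, data must also be on or before the day of first dose of OL active study drug". None of these places mentions the time of the dose.

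**Protocol.** The synopsis says that on OL Day 1 "subjects will not return for a visit; rather, the subjects will be instructed to take their first dose of ABT-493/ABT-530 at home". Section 5.1.3 agrees on timing: drug is dispensed at the final double-blind visit and "Administration of ABT-493/ABT-530 will start the next day (OL Day 1"). Footnote b of the Appendix C open-label table collects the start date by telephone: "The site will call the subject and record the study drug start date in the EDC system and source documents". Yet that same table marks Day 1 for vital signs, safety laboratories, HCV RNA, HIV-1 RNA, HCV resistance, archive plasma and both PK rows, among them "Pharmacokinetic Samples for subjects who do not participate in the Optional Intensive PK sampling". For subjects outside intensive PK, section 5.3.2.1 says the reverse: "At all DB and OL Treatment Period visits, except for Day 1, a single blood sample (3 mL) will be collected for ABT-493/ABT-530".

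**The concern.** Two programmers could follow the SAP faithfully and choose different placebo values for the same subject. Under the tables, a sample from a day on which active drug is taken can be filed as placebo data, even if it was drawn after the dose. It would then sit on the placebo side of the Arm A versus Arm B comparisons of laboratory and vital-sign change in SAP 11.3.2 and 11.4.2. For co-infected subjects it would enter the double-blind HIV-1 RNA summary in SAP 11.5.

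This matters only if someone is sampled on OL Day 1. The protocol leaves that open, because a site working from the Appendix C table and a site working from the synopsis would do different things.

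**Working it through.** No sample size, power or alpha figure depends on this point, so there is no figure of the plan's to reproduce. The check counts the Appendix C marks and then applies each cut-off to the same subject.

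**1. Can an OL Day 1 sample exist?** The Appendix C open-label table has 17 rows, of which 12 are marked on Day 1. Leaving out the first-dose row gives 11 of 16. The five unmarked rows are physical examination, ECG, pregnancy test, dispensing and flow cytometry. No footnote assigns the 11 marks to the double-blind end-of-treatment visit.

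**2. The two rules.** Let V be the day of the final double-blind visit, L the last placebo day and O = V + 1 the day of the first open-label dose (protocol 5.1.3).

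- Tables 4 and 8: a sample on day d counts if d ≤ L + 2 and d ≤ O.
- SAP 6.1.2: a sample on day d counts if d ≤ L + 2 and d < O.
- Final DB value: the last eligible sample.
- Week 8 value: the eligible sample in Days 43 to 70 that is closest to Day 56.

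**3. Applied to samples on V and on O.** V is assumed to run from 54 to 58, with L = V or L = V − 1. OL Day 1 is then DB Study Drug End Day 1 or 2, so the End Day 2 limit is met in all 10 combinations. Both values of L give the same selections.

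| V | O | Final value, tables | Final value, 6.1.2 | Week 8 value, Table 4 |
|---|---|---|---|---|
| 54 | 55 | Day 55 | Day 54 | Day 55 (OL Day 1) |
| 55 | 56 | Day 56 | Day 55 | Day 56 (OL Day 1) |
| 56 | 57 | Day 57 | Day 56 | Day 56 |
| 57 | 58 | Day 58 | Day 57 | Day 57 |
| 58 | 59 | Day 59 | Day 58 | Day 58 |

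The final value differs between the rules in 10 of 10 combinations. The Week 8 value is the OL Day 1 sample in 4 of 10 (two visit days × two values of L). In general this happens when |V + 1 − 56| < |V − 56|, that is, when V ≤ 55.

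**4. Where the rules agree.** Take O = 57. With L = 30 the limit is Day 32 and with L = 54 it is Day 56, so both rules exclude the sample. With L = 55 or 56 the limit is Day 57 or 58, so the tables admit it and 6.1.2 does not. A subject who stopped placebo early and waited for open-label treatment is therefore not affected.

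**5. After aligning the bound.** With d < O in both places, the final double-blind visit sample is selected in all 10 combinations.

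**The case against.** The no-visit reading has most of the text behind it. The synopsis lists open-label visits from Week 1, sections 5.1.3 and 5.5.1 have the site telephone the subject, and SAP Table 9 has no OL Day 1 row. If nobody attends, the SAP discrepancy rarely bites. That stands, and it makes 168 (the planned size of Arm B) a ceiling rather than an expected number.

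The consequences are also narrow. Efficacy is analysed in Arm A unless otherwise specified. SAP 11.2.1 already cuts Arm B double-blind adverse events before OL Day 1, the Arm B resistance baseline is the last sample before OL Day 1, and patient-reported outcomes are not collected in the open-label period. All of that stands.

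The inclusive bound may also have a purpose: it keeps a genuine pre-dose sample from the final double-blind visit if the subject takes the dispensed open-label drug that same day. The SAP does not give this reason, but a blanket cut before OL Day 1 would lose such a sample, and the fix should avoid that.

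Three stronger readings are tempting but not supported:

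- A reader might infer that Appendix C schedules a complete visit on OL Day 1. Five rows are unmarked.
- A reader might infer that 5.3.2.1 bars a Day 1 PK sample for everyone. The exception is written for subjects outside intensive PK. For intensive-PK subjects the text names DB Day 1 and the Week 4 visits, then asks for one sample at all other visits without excepting OL Day 1.
- A reader might infer that every subject with an OL Day 1 sample has the placebo final value replaced. The End Day 2 limit prevents that for those who stopped placebo earlier.

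None of this removes the conflict between 6.1.2 and footnote c, which define the same quantity with different bounds.

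**Conclusion.** The inconsistency is real and worth correcting, but it does not threaten the trial's main result. For an Arm B subject with samples at the final double-blind visit and on OL Day 1, where OL Day 1 is no later than DB Study Drug End Day 2, the tables and 6.1.2 always choose different final values. Table 4 also moves the Week 8 value when the double-blind visit was on Day 55 or earlier.

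The direct contradiction concerns the Final DB Treatment Value, since that is all 6.1.2 defines. For the other double-blind windows, the fault is that the Notes admit the active-dosing day without a pre-dose condition.

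Exposure is limited to Arm B subjects actually sampled on OL Day 1, at most 168, and to laboratory, vital-sign and HIV-1 RNA summaries. The documents do not say how far any parameter moves after one dose. I assume the shift is small for most, so a material bias in the safety comparison is not shown. The result rests on taking the Appendix C marks at face value and on open-label dosing starting the day after the final double-blind visit.

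**What to change.** **SAP.** Use one Arm B boundary in 6.1.2 and in footnote c and the Notes of Tables 4 and 8: only samples collected before the first open-label active dose count as double-blind data. Apply it by date and time where both are available. Otherwise require the sample to be dated before OL Day 1, except that a sample from the final scheduled double-blind visit is kept as pre-dose. The date fallback will probably be needed often, because footnote b of the Appendix C open-label table asks the site to record a start date, not a time.

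**Protocol.** The synopsis, section 5.3.2.1 and the Day 1 column of the Appendix C open-label table contradict one another and must be reconciled to one schedule.

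**Cost.** A few lines of SAP text and a protocol clarification, with no effect on sample size or on the primary analysis. The downside is that OL Day 1 samples not shown to be pre-dose are not used in double-blind summaries. For HIV-1 RNA such a sample would then fall in no window, since Table 9 starts at Day 2.
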